
## 15 Safety Reporting

The Principal Investigator is responsible for ensuring that all site staff involved in this study are familiar with the content of this section.

All SAEs must be reported immediately (and within 24 hours of knowledge of the event) by the PI/local researcher at the participating site to the CTR unless the SAE is specified as not requiring immediate reporting (see section 15.2).

### 15.1 Definitions

Term	Definition
Adverse Event (AE)	For the purpose of this study an adverse event will be defined as only the specific AEs as detailed in section 15.2.
Serious Adverse Event (SAE)	Any adverse event that - 

• Results in death

• Is life-threatening*

• Required hospitalisation or prolongation of existing hospitalisation**

• Results in persistent or significant disability or incapacity

• Consists of a congenital anomaly or birth defect

• Other medically important condition***

**\*Note:** The term 'life-threatening' in the definition of serious refers to an event in which the study participant was at risk of death at the time of the event or it is suspected that used or continued use of the product would result in the subject's death; it does not refer to an event which hypothetically might have caused death if it were more severe.

**\*\* Note:** Hospitalisation is defined as an inpatient admission, regardless of the length of stay, even if the hospitalisation is a precautionary measure for continued observation. Pre-planned hospitalisation e.g. for pre-existing conditions which have not worsened, or elective procedures, does not constitute an SAE.

**\*\*\* Note:** other events that may not result in death, are not life-threatening, or do not require hospitalisation, may be considered as an SAE when, based upon appropriate medical judgement, the event may jeopardise the participant and may require medical or surgical intervention to prevent one of the outcomes listed above.

An SAE occurring to a research participant should be reported to the main REC where in the opinion of the CI the event was:

- Related – that is, it resulted from administration of any of the research procedures, and
- Unexpected – that is, the type of event is not listed in the protocol as an expected occurrence

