## 15.2 Study Specific AE reporting requirements

For the purposes of this study the following events will be considered AEs and must be captured on the CRF form.

- Urinary tract infection
- Haematuria
- Urinary retention
- Discomfort
- Dysuria

These should be completed in the participant's notes and on the AE reporting CRF page and forwarded to the CTR in the normal timeframes for CRFs.

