## 15.3 Study Specific SAE Reporting requirements

In addition to the SAE reporting requirements above, for the purposes of this study the following events will also be considered SAEs and must be captured on the SAE form and reported to the CTR PriMUS Study Team within 24 hours of knowledge of the event:

- Urethral trauma requiring intervention

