**Table 4: Expected Adverse Events from Urodynamic Procedure**

Expected Adverse Events From Urodynamic Procedure			
Adverse Event	Mild	Moderate	Severe
Urinary Tract Infection	Transient symptoms not requiring action	Persistent symptoms requiring participant to be seen by HCP with or without treatment (such as course of antibiotics)	Needing hospitalisation
Visible haematuria	Transient symptoms not requiring action	Persistent symptoms requiring participant to be seen by HCP with or without treatment (such as course of antibiotics)	Needing hospitalisation
Urinary retention	Transient symptoms not requiring action	Persistent symptoms requiring participant to be seen by HCP with or without treatment (such as course of antibiotics)	Needing hospitalisation

Discomfort on passing urine	Transient symptoms not requiring action	Persistent symptoms requiring participant to be seen by HCP with or without treatment (such as course of antibiotics)	Needing hospitalisation
Urethral trauma during insertion or removal of catheter for urodynamic procedure	Transient symptoms not requiring action	Persistent symptoms requiring participant to be seen by HCP with or without treatment (such as course of antibiotics)	Needing hospitalisation

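### The closed adverse event list omits urethral trauma, so catheter injury that needs no intervention is not counted under its own name

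*Protocol*

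**What the plan says.** Four places in section 15 of the Protocol bear on this point.

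- **15.1 Definitions** restricts the term: "For the purpose of this study an adverse event will be defined as only the specific AEs as detailed in section 15.2". A serious adverse event is then an adverse event that meets a seriousness criterion.
- **15.2 Study Specific AE reporting requirements** introduces its list with "For the purposes of this study the following events will be considered AEs and must be captured on the CRF form". The list has five entries: urinary tract infection, haematuria, urinary retention, discomfort and dysuria.
- **15.3 Study Specific SAE Reporting requirements** adds one further serious event, reportable within 24 hours: "Urethral trauma requiring intervention". The protocol does not define intervention.
- **15.4 Expectedness** refers to Table 4, titled "Expected Adverse Events from Urodynamic Procedure". Its fifth row is "Urethral trauma during insertion or removal of catheter for urodynamic procedure". Like the other rows, it has a mild grade (transient, no action needed), a moderate grade ("Persistent symptoms requiring participant to be seen by HCP with or without treatment") and a severe grade ("Needing hospitalisation").

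Adverse events are collected at the 3 Day Follow Up Phone Call (section 11) and again at the 3-6 month follow-up (11.3). Neither place widens the definition.

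**The concern.** Urethral injury is a direct harm of the invasive reference test that every participant undergoes for the study. The protocol recognises it as an expected event and grades it down to cases that need no action. Its own definition, which admits *only* the 15.2 list, nevertheless says that such an injury is not an adverse event unless it triggers the 15.3 rule.

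The amendment history gives the aim of the narrowed definition as collecting events related to the study. (It is cited here for that aim only, not as a discrepancy.) An injury from the study catheter is such an event, so leaving it off the list works against the aim. At stake is a usable count: as written, the study could not report how many men had urethral trauma short of intervention. Sites could also differ in what they report, since each must decide for itself what counts as intervention.

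**Working it through.** No figure in the protocol needs to be reproduced. The check is a comparison of lists.

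**Step 1: Table 4 against 15.2.**

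| Table 4 event | Counterpart in 15.2 |
|---|---|
| Urinary tract infection | Urinary tract infection |
| Visible haematuria | Haematuria |
| Urinary retention | Urinary retention |
| Discomfort on passing urine | Discomfort (and dysuria) |
| Urethral trauma at catheter insertion or removal | None |

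Four of the five events have a counterpart, so 5 − 4 = 1 does not.

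**Step 2: what 15.3 recovers, by grade of trauma.**

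- *Mild.* By Table 4 no action is needed, so there is no intervention. It is neither an adverse event under 15.1 and 15.2 nor a serious event under 15.3.
- *Moderate, treated.* If treatment counts as intervention, 15.3 applies and the event is reported as serious.
- *Moderate, seen but not treated.* Table 4 allows for this case. If being seen is not an intervention, the event falls outside both lists. If any contact with a health professional counts, 15.3 covers it.
- *Severe.* Admission is naturally read as intervention, so 15.3 applies.

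Of the three grades of trauma, one (mild) is always unnamed. A second (moderate) is partly unnamed, unless contact with a health professional alone is taken as intervention.

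**Step 3: what still reaches the record.** Trauma that causes bleeding, painful voiding, discomfort or retention is recorded under that symptom, because all four are in 15.2. Trauma with none of these need not be entered on the CRF. The symptom entries cannot be turned back into a trauma count, since the same symptoms can arise after catheterisation without a recognised injury.

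**Step 4: number of men.** The plan is for 880 participants. The protocol gives no rate of urethral trauma, so no number affected is derived.

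**The case against.** The strongest reply is that Table 4 serves another purpose. Section 15.4 uses it to judge whether a serious event was expected. Because 15.3 makes urethral trauma a serious event when intervention is needed, Table 4 has to list trauma, and its natural partner is 15.3 rather than 15.2. Table 4 grades trauma by symptoms, and 15.2 already collects the symptoms that minor trauma would produce. Narrowing the adverse event list was a deliberate amendment. No primary or secondary objective or outcome in sections 5.1 to 5.4 estimates a complication rate, and the study is classed as low risk.

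Much of this stands. Table 4 and 15.2 need not match line by line, most of the harm would be recorded in some form, and no stated aim is defeated. It does not answer the narrower point. Table 4 shows that the authors foresaw trauma in mild and moderate forms, and the closed definition leaves no place to record those forms by name. This is the result of a stated rule, not of detail left to another document.

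Two stronger readings are tempting. A reader might infer that trauma leading to admission escapes serious event reporting. That requires admission not to count as intervention, which is strained: 15.1 counts an inpatient stay as hospitalisation "even if the hospitalisation is a precautionary measure for continued observation", and a listed symptom that leads to admission is a serious event in its own right. A reader might also infer from the 3 Day Follow Up Phone Call that a man with retention would be told to start the home flow meter, since infection is the only stated reason to hold it. That rests mostly on silence. The call has its own CRF and sites have a manual, neither of which is shown; each hub has a urology champion for urgent queries; and any effect on the flow data is unknown.

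**Conclusion.** The point holds in a limited form. Read together, 15.1 to 15.3 leave urethral trauma without intervention uncounted under its own name: all mild cases, and moderate cases seen but not treated. It is one of five Table 4 events.

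The conclusion assumes that *only* in 15.1 is meant literally, that treatment or admission counts as intervention, and that being seen without treatment does not. If being seen does count, the gap shrinks to mild trauma alone. It also assumes that the adverse event CRF, which is not shown, follows 15.2.

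The practical loss is modest. The documents do not support a claim that the harm goes wholly unrecorded, that serious trauma is missed, or that sensitivity, specificity or the prediction models are affected. The change is still worth making, because the event is a direct harm of the reference test and naming it costs very little.

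**What to change.** Add the Table 4 term, "Urethral trauma during insertion or removal of catheter for urodynamic procedure", to the 15.2 list with the words *any grade*. Keep trauma requiring intervention as a serious event in 15.3. Check that the adverse event and day-3 call CRFs carry the new term.

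The cost is one line of protocol text and that check. The drawback is double entry, since one injury may be recorded both as trauma and as its symptom. Safety tables should therefore count men and events separately.

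At most, and as an option, one sentence could be added to the 3 Day Follow Up Phone Call: the flow meter is not started while a listed adverse event such as retention is unresolved. A fuller set of triage rules is operational detail and is not needed in the protocol.

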## 15.2 Study Specific AE reporting requirements

For the purposes of this study the following events will be considered AEs and must be captured on the CRF form.

- Urinary tract infection
- Haematuria
- Urinary retention
- Discomfort
- Dysuria

These should be completed in the participant's notes and on the AE reporting CRF page and forwarded to the CTR in the normal timeframes for CRFs.

## 15.3 Study Specific SAE Reporting requirements

In addition to the SAE reporting requirements above, for the purposes of this study the following events will also be considered SAEs and must be captured on the SAE form and reported to the CTR PriMUS Study Team within 24 hours of knowledge of the event:

- Urethral trauma requiring intervention

### 15.3 Causality

Causal relationship will be assessed for the clinical and data collection procedures. For AEs, this assignment should be made by the PI or the delegated research nurse. For SAEs this assignment should be made by the PI or delegated research nurse and the assessment confirmed by the Chief Investigator or a delegated Clinical Reviewer.

Relationship	Description	Reasonable possibility that the SAE may have been caused by the intervention?
Unrelated	There is no evidence of any causal relationship with the study/intervention	No
Unlikely	There is little evidence to suggest there is a causal relationship with the study/intervention (e.g. the event did not occur within a reasonable time after administration of the study medication). There is another reasonable explanation for the event (e.g. the participant's clinical condition, other concomitant treatment).	No
Possible	There is some evidence to suggest a causal relationship with the study/intervention (e.g. because the event occurs within a reasonable time after administration of the study medication). However, the influence of other factors may	Yes

	have contributed to the event (e.g. the participant's clinical condition, other concomitant treatments).	
Probable	There is evidence to suggest a causal relationship and the influence of other factors is unlikely.	Yes
Definite	There is clear evidence to suggest a causal relationship and other possible contributing factors can be ruled out.	Yes

The causality assessment given by the Principal Investigator (or delegate) cannot be downgraded by the Chief Investigator (or delegate), and in the case of disagreement both opinions will be provided.

#### 15.4 Expectedness

The Chief Investigator(s) (or another delegated appropriately qualified individual) will assess each SAE to perform the assessment of expectedness. Expectedness decisions can be guided by the information in Table 4 below; other factors such as the participant population and participant history should not be taken into account. Expectedness is not related to what is an anticipated event within a particular disease. SAEs which add significant information on specificity or severity of a known, already documented adverse event constitute unexpected events. For example, an event more specific or more severe than that described in the table below is considered unexpected.

**Table 4: Expected Adverse Events from Urodynamic Procedure**

Expected Adverse Events From Urodynamic Procedure			
Adverse Event	Mild	Moderate	Severe
Urinary Tract Infection	Transient symptoms not requiring action	Persistent symptoms requiring participant to be seen by HCP with or without treatment (such as course of antibiotics)	Needing hospitalisation
Visible haematuria	Transient symptoms not requiring action	Persistent symptoms requiring participant to be seen by HCP with or without treatment (such as course of antibiotics)	Needing hospitalisation
Urinary retention	Transient symptoms not requiring action	Persistent symptoms requiring participant to be seen by HCP with or without treatment (such as course of antibiotics)	Needing hospitalisation

Discomfort on passing urine	Transient symptoms not requiring action	Persistent symptoms requiring participant to be seen by HCP with or without treatment (such as course of antibiotics)	Needing hospitalisation
Urethral trauma during insertion or removal of catheter for urodynamic procedure	Transient symptoms not requiring action	Persistent symptoms requiring participant to be seen by HCP with or without treatment (such as course of antibiotics)	Needing hospitalisation

## 15.5 Reporting procedures

### 15.5.1 Participating Site Responsibilities

The PI (or delegated research nurse from the study team registered on the delegation log) should sign and date the SAE CRF to acknowledge that he/she has performed the seriousness and causality assessments. Investigators should also report SAEs to their own health boards or trust in accordance with local practice.

A completed SAE form for all events requiring immediate reporting should be submitted via fax or email to the CTR PriMUS Study Team within 24 hours of knowledge of the event. A separate form must be used to report each event, irrespective of whether or not the events had the same date of onset.

The participant will be identified only by study number, date of birth and initials. The participant's name should not be used on any correspondence.

It is also required that sites respond to and clarify any queries raised on any reported SAEs and report any additional information as and when it becomes available through to the resolution of the event. Additionally, the CTR may request additional information relating to any SAEs and the site should provide as much information as is available to them in order to resolve these queries.

**Serious Adverse Event (SAE) email address:**

**[[contact]](mailto:[contact])**

**SAE [contact]**

Serious adverse events should be reported from time of signature of informed consent, throughout the treatment period up to, and including 7 days after the participant receives the urodynamic assessments.

An SAE form is not considered as complete unless the following details are provided:

- Full participant study number
- The adverse event
- A completed assessment of the seriousness, and causality as performed by the PI (or delegated research nurse from the study team).

If any of these details are missing, the site will be contacted and the information must be provided by the site to the CTR within 24 hours.

[figure not shown]
All other AEs should be reported on the CRF following the CRF procedure described in Section 15.

#### **15.5.2 The CTR responsibilities**

Following the initial report, all SAEs should be followed up to resolution wherever possible, and further information may be requested by the CTR. Follow up information must be provided on a new SAE form. The CTR should continue reporting SAEs until 7 days after the participant receives the urodynamic reference test. Once an SAE is received at the CTR, it will be evaluated by staff at the CTR and sent to the Chief Investigator(s) (or their delegate) for an assessment of expectedness.

CTR will notify the main REC of all related and unexpected SAEs (i.e. all unexpected SARs) occurring during the study within **15** calendar days of the CI becoming aware of the event. All SAEs and SARs will be reported to the monitoring committees (SMG and SSC) as required by the relevant committee/party. All unrelated SAEs will be reported to the SMG and SSC, and any arising safety concerns will also be reported to the main REC as part of the annual progress report.

SAE Flowchart (Figure 3)

[figure not shown]
## 15.6 Urgent Safety Measures (USMs)

An urgent safety measure is an action that the Sponsor, Chief Investigator or Principal Investigator may carry out in order to protect the subjects of a study against any immediate hazard to their health or safety. Any urgent safety measure relating to this study must be notified to the Research Ethics Committee immediately by telephone, and in any event within 3 days in writing, that such a measure has been taken. USMs reported to the CTR will be handled according to CTR processes.

## 16 Statistical Considerations

### 16.1 Sample size

*Development cohort:* We will fit three separate dichotomous logistic regression models (Figure 2) to predict the presence of each of the conditions: Bladder outlet obstruction (BOO), detrusor overactivity (DO), and detrusor underactivity (DU).

**Figure 2:** Modelling strategy based on separate dichotomous logistic regression models. BOO, bladder outlet obstruction; DO, detrusor overactivity; DU, detrusor underactivity; LUTS, lower urinary tract symptoms.

Sample sizes for developing predictive models are typically based on ensuring that overfitting does not occur, and are based on rules of thumb discerned from simulation studies. The most commonly used rule suggests 10 events are required per predictor and was based on two simulation studies. Vittinghoff and McCulloch have undertaken more extensive evaluation, and suggest that this rule of thumb may be too conservative and can be relaxed as other factors are likely to be equally or more important than the number of events per predictor [12]. They suggest that events per predictor values (EPV) of between 5 and 9 may be justified. Of the four diagnosis categories, the lowest prevalence is estimated at 16% for DU, such that a sample of 350 would provide 56 events – enough assuming EPV = 5 for up to 11 variables to be fitted as required. Over 100 events would be expected for the BOO model and 200 for the DO model providing more than adequate events.

*Validation cohort:* The sample size for the validation study is determined by ensuring that estimates of test accuracy (particularly sensitivity) are made with adequate precision. Based on a sample size of

325, estimates of a sensitivity of 75% for DU, BOO and DO will be based on samples of 52, 101 and 185, and made within confidence limits of 14%, 10% and 8% respectively (based on the lower limit of the 95% confidence interval for an observed proportion of 0.75). Should the test be more sensitive, the confidence intervals will be narrower. Estimates of specificity for DU, BOO and DO will be based on samples of 273, 224 and 140 respectively. In the same way a specificity of 75% would be estimated within 6%, 7% and 8% intervals.

To complete the study we require 675 complete data sets. We plan to screen 3520 men with an expected 25% (880 men) agreeing to take part. This allows an attrition rate of a further 20-25% of these to achieve 675 complete datasets; 350 in the development cohort and 325 in the validation cohort.

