## **6 Study Design and Setting**

### **6.1 Design**

We plan a prospective diagnostic accuracy study to determine which of a number of simple clinical variables (index tests) collected in primary care and used individually or in combination best predict urodynamic diagnosis in men who present to their GP with lower urinary tract symptoms (LUTS). Two cohorts of participants will undergo the series of simple index tests and the invasive reference test (urodynamics) in community settings. We aim to recruit 880 men from primary care to the study.

The study will follow the NICE pathway for LUTS as standard (<http://www.nice.org.uk/guidance/cg97>) [1]. Study participants will undergo standard assessment recommended for primary care by NICE. In addition, urine flow rate and residual urine estimation (optional in the NICE pathway and not routine in primary care) will be included. All men in the study will undergo urodynamics as the reference test for diagnostic accuracy; this is a specialist test in the NICE pathway. All results will be given to the GP with the likely diagnosis and recommended management options to decide on further care.

Test variables collected from the first cohort will be used to develop a statistical model which will combine results from the index tests to best predict urodynamic diagnosis from the reference test. The diagnostic accuracy of the model will then be ascertained using the results from the second cohort. A qualitative study will explore the feasibility of creating and introducing a decision aid based on the statistical model for use in primary care, including potential acceptability to primary care staff and patients.

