**Table 3: Progression Criteria**

[figure not shown]
Criteria	Level	Action
Site Recruitment	30 sites open	Monitor site recruitment and time to first recruit. At least 0.3 patients per practice per month.  Discuss potential mitigating strategies
Recruitment rate*	70 %  40 – 70%  < 40%	GO  Discuss potential mitigating strategies  STOP?
Gold standard undertaking (and evaluable?)	70 %  50 – 70%  <50%	GO  Discuss potential mitigating strategies  STOP?
Acceptability of gold standard urodynamic assessment	Qualitative interviews	

*\*Allowing for 2 –month lag phase*

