### 13.1 Recruitment rates

We plan to screen an average of 147 and recruit 37 men per month on average during recruitment with predicted numbers lower in initial, and higher in later phases of recruitment. From CPRD 2014 data we estimate an incidence of four men per practice per month. Target accrual rates are presented in the Figure below:

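### The upper end of the 20-25% attrition allowance is not covered: 880 recruits tolerate at most 23.3% loss if 675 complete datasets are required

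*Protocol*

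**What the plan says.** Protocol section 16.1 builds the recruitment target in three steps. It fixes the requirement: "To complete the study we require 675 complete data sets", made up of "350 in the development cohort and 325 in the validation cohort". It fixes recruitment: "We plan to screen 3520 men with an expected 25% (880 men) agreeing to take part". It then links the two: "This allows an attrition rate of a further 20-25% of these to achieve 675 complete datasets". Section 6.1 repeats the target of 880.

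The two cohort sizes carry the other figures in section 16.1. For development, "the lowest prevalence is estimated at 16% for DU, such that a sample of 350 would provide 56 events", which the section sets against five events per variable and up to 11 variables. For validation, 325 men are expected to include 52, 101 and 185 with detrusor underactivity (DU), bladder outlet obstruction (BOO) and detrusor overactivity (DO). A sensitivity of 75% is then said to be estimated to within 14%, 10% and 8%, judged by the lower 95% confidence limit.

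**The concern.** An attrition allowance tells the sponsor and the steering committee how much loss the recruitment target can bear, so its upper end is the figure people rely on. Here the upper end is 25%, and taking 25% off 880 does not leave 675. The section calls 675 a requirement and also says that the allowance reaches 25%. At 880 recruits both statements cannot be true.

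The number of DU events for model development and the precision of the validation estimates both rest on the split of 675. A committee watching attrition drift towards 25% would believe that the design still held when it was already slightly short.

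**Working it through.** **Inputs, all from Protocol section 16.1.** Screened 3520; agreeing 25%; recruited 880; complete datasets required 675, as 350 + 325; attrition 20-25%. Prevalence of DU is 16% (section 16.1); BOO 31% and DO 57% come from section 4.

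**Reproducing the plan's own figures.** 3520 x 0.25 = 880 and 350 + 325 = 675, both exact. As a cross-check, section 13.1 gives 147 screened and 37 recruited per month. Over 24 months that is 147 x 24 = 3528 and 37 x 24 = 888, in line with 3520 and 880. The pair of 880 recruited and 675 complete implies attrition of 1 - 675/880 = 23.3%, which lies inside the stated range.

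**Complete datasets left from 880, as 880 x (1 - d).**

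| Attrition d | Complete | Against 675 |
|---|---|---|
| 20% | 704 | +29 |
| 22.5% | 682 | +7 |
| 23.3% | 675 | 0 |
| 25% | 660 | -15 (2.2%) |

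**Recruits needed for 675, as 675/(1 - d).** At 20%: 844. At 22.5%: 871. At 25%: 675/0.75 = 900, which is 20 more than planned and, at 25% agreement, means screening 900/0.25 = 3600.

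**What 660 would mean.** The protocol does not say how a shortfall would be divided between the cohorts, so two cases are shown. Both treat the number of complete datasets as the number analysed.

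*Case 1, all 15 lost from validation (assumption).* Validation has 660 - 350 = 310 men. Expected cases are 310 x 0.16 = 50 DU, 310 x 0.31 = 96 BOO and 310 x 0.57 = 177 DO. The table gives the distance from an observed 75% down to the exact (Clopper-Pearson) lower 95% limit, in percentage points.

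| Condition | Stated | n = 325 | n = 310 |
|---|---|---|---|
| DU | 14 | 13.95 | 14.3 |
| BOO | 10 | 9.6 | 9.9 |
| DO | 8 | 6.9 | 7.1 |

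In whole percentages, as the protocol reports them, the values at 310 are 14, 10 and 7. None is worse than stated. With a Wilson interval instead, DU moves from 13.2 (52 cases) to 13.5 (50 cases).

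*Case 2, loss shared in proportion.* Development has 660 x 350/675 = 342 men and 342 x 0.16 = 55 DU events, against 56 stated. Eleven variables at five events each need 55. Validation has 660 x 325/675 = 318 men and 318 x 0.16 = 51 DU cases, against 52 stated.

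**The case against.** The strongest reply is that the range is merely rounded loosely. It brackets the exact break-even of 23.3%, most of it delivers 675 or more, and the worst miss is 15 men. This largely stands: the recruitment target of 880 is reproducible, and there is no sample-size error behind it. It does not rescue the sentence, because the section says that 25% is allowed and it is not.

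A second reply is that incomplete records are not all lost. Section 16.5 keeps everyone with reference test data, and sections 16.2 and 17.1 impute missing values. A man with urodynamics but a missing index test therefore counts as attrition from complete datasets yet stays in the analysis. This also stands, and it softens the consequence further. It does not help for men without urodynamics, whom section 16.5 does not include.

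Two stronger readings are tempting, and the protocol does not support either:

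- **Stated precision is missed.** A reader might infer that the 14% for DU sensitivity fails at 25% loss, because 14.3 exceeds 14. The protocol gives whole percentages, and 14.3 rounds to 14 even with the whole shortfall placed on validation.
- **The pilot threshold is wrong.** A reader might set the 70% GO level for "Gold standard undertaking (and evaluable" in Table 3 beside section 16.1, note that 70% of 880 is only 616, and conclude that the threshold must rise. Table 3 is a feasibility trigger for the internal pilot. Section 16.1 does not offer it as the attrition assumption, and a pilot threshold may reasonably sit below the final requirement. Where to put it is a design choice and has no bearing on this arithmetic.

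**Conclusion.** The point holds for the upper end of the range only. Recruiting 880 covers attrition of up to 23.3%. Between 23.3% and 25% the plan falls short of its own requirement, by at most 15 complete datasets (2.2%). That follows from the stated figures and needs no assumption.

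A reader might infer that the allowance as a whole fails; it does not, since losses of 20% to 23.3% leave 704 to 675. The practical effect is slight: about 0.4 points of precision for DU sensitivity in the less favourable division, or about one DU event in development if the loss is shared. Those two figures rest on the assumed division of the shortfall, on the protocol's prevalences, and on counting only complete datasets as analysed. This is a false statement about a required number. It does not show the study to be too small.

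**What to change.** In section 16.1, do one of the following:

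- Restate the allowance as up to about 23%, the loss at which 880 recruits still give 675 complete datasets.
- Keep 20-25% and state that it yields 660 to 704 complete datasets. One added sentence could say that 660 leaves the stated precision unchanged at whole-percentage rounding.

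Either is a change of wording, with no extra participants and no change to the analysis. The first makes the published tolerance slightly less generous. If the study team does want 25% covered with 675 guaranteed, the target becomes 900, at a cost of 20 more recruits and 80 more men screened (3600 against 3520). The small effect on precision does not call for that.

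No change to Table 3 is needed. For information only, 675/880 corresponds to 77% completion.
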